### Background and Scientific Rationale

Financial market volatility, digital information exposure, economic uncertainty, and prolonged media consumption may contribute to measurable physiologic stress responses and behavioral alterations. Emerging wearable biosensor technologies permit continuous remote monitoring of autonomic nervous system metrics, sleep characteristics, cardiovascular parameters, and behavioral indicators associated with stress exposure. This decentralized observational study is designed to evaluate physiologic and behavioral responses associated with financial and informational stress environments using wearable biosensor monitoring systems and validated psychometric instruments.

### Primary Objective

To evaluate changes in autonomic and physiologic stress biomarkers associated with financial and informational stress exposure over time.

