### Study Design

This study is a prospective decentralized observational study utilizing wearable biosensor monitoring and validated psychometric questionnaires. Participants will undergo remote physiologic monitoring during routine daily activities and periods of financial or informational stress exposure. Commercially available wearable devices may be utilized to collect:

- Heart rate variability

- Resting heart rate
- Sleep duration
- Sleep efficiency
- Electrodermal activity
- Activity metrics

Validated questionnaires including the Generalized Anxiety Disorder-7 (GAD-7) and Perceived Stress Scale-10 (PSS-10) may be administered electronically during scheduled study intervals.

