## Study Population

Adult participants exposed to varying levels of financial market activity, occupational stress, economic stress environments, and digital media exposure may be enrolled.

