**Statistical Analysis Plan**

Descriptive statistics will summarize baseline physiologic and demographic characteristics. Continuous physiologic variables including heart rate variability, sleep duration, sleep efficiency, resting heart rate, and galvanic skin response will be analyzed using longitudinal repeated-measures approaches and mixed-effects regression models where appropriate. Psychometric questionnaire outcomes including GAD-7 and PSS-10 scores will be analyzed longitudinally across study intervals. Correlation analyses may evaluate associations between physiologic biomarkers and psychometric stress measures. Missing data may be addressed through mixed-model maximum likelihood estimation or multiple imputation methods depending on missingness patterns. Statistical significance will utilize a two-sided alpha threshold of 0.05.

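### The primary objective is about financial and informational stress exposure, but the protocol neither specifies how that exposure is measured nor relates any outcome to it

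*Protocol*

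**What the plan says.** The Primary Objective reads: "To evaluate changes in autonomic and physiologic stress biomarkers associated with financial and informational stress exposure over time". Two other sections refer to exposure:

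- **Study Design** places two kinds of time side by side, "remote physiologic monitoring during routine daily activities and periods of financial or informational stress exposure", but does not say how one is told from the other.
- **Study Population** describes adults "exposed to varying levels of financial market activity, occupational stress, economic stress environments, and digital media exposure". This states who may enrol. It does not say that the level is recorded.

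For data collection, Study Design says "Commercially available wearable devices may be utilized to collect" six items: heart rate variability, resting heart rate, sleep duration, sleep efficiency, electrodermal activity and activity metrics. It adds: "Validated questionnaires including the Generalized Anxiety Disorder-7 (GAD-7) and Perceived Stress Scale-10 (PSS-10) may be administered electronically during scheduled study intervals".

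For analysis, the Statistical Analysis Plan section says the continuous physiologic variables "will be analyzed using longitudinal repeated-measures approaches and mixed-effects regression models where appropriate". GAD-7 and PSS-10 are to be analysed longitudinally over the study intervals. The only association it names is between physiologic biomarkers and psychometric scores.

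**The concern.** An association needs both sides measured, and only the outcome side is specified. A team following this text would estimate how HRV, sleep duration, resting heart rate and PSS-10 change with time on study, and would then have to attribute that change to an exposure for which the protocol plans no record.

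Several ordinary processes move these outcomes over time without any financial or informational stress: regression to the mean, season, getting used to the device, and answering the same questionnaire repeatedly. Without a recorded exposure to set the outcomes against, these cannot be told apart from a response to exposure. The primary question is at stake, not a detail of its analysis. Individual media use in particular is hard to reconstruct reliably once the observation period is over.

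**Working it through.** **Document check.** The protocol states no figure on this point, so there is none to reproduce. The check is whether any planned data item or model term represents financial or informational exposure.

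| Where | Items | Measuring exposure |
|---|---|---|
| Study Design, wearable data | 6 | 0 |
| Study Design, named questionnaires (GAD-7, PSS-10) | 2 | 0 |
| Primary outcomes (HRV, sleep duration, resting heart rate, PSS-10) | 4 | 0 |
| Secondary outcomes (sleep efficiency, GSR, GAD-7) | 3 | 0 |
| Statistical Analysis Plan, exposure terms or period contrasts | none named | 0 |

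The eligibility criteria add no exposure level, stratum or group. PSS-10 and GAD-7 cannot stand in for exposure: they record perceived stress and anxiety from any source, and both are outcomes, so using them as the exposure would be circular. The planned biomarker-psychometric correlations relate one outcome to another and serve a secondary objective.

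**Illustration of false attribution.** Every input here is an assumption except the two-sided 0.05 level, which comes from the Statistical Analysis Plan section. The protocol gives no sample size, SD, reliability or baseline shift. Take no true exposure effect, a baseline mean that lies s SD from participants' usual level, test-retest correlation r, n participants, and one before-after comparison.

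- Expected spurious change, in SD units: (1 − r) × s
- Standard error: √(2(1 − r)/n)
- z = change / standard error
- Chance of significance: Φ(z − 1.96) + Φ(−z − 1.96)

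For n = 200 and s = 0.5:

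- r = 0.6: 0.20 / 0.0632, z = 3.16, 88.5%
- r = 0.7: 0.15 / 0.0548, z = 2.74, 78.2%
- r = 0.8: 0.10 / 0.0447, z = 2.24, 60.9%

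With n and s varied in the same formula:

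| n | Baseline shift (SD) | r = 0.8 | r = 0.6 |
|---|---|---|---|
| any | 0 | 5% | 5% |
| 200 | 0.10 | 7.3% | 9.7% |
| 50 | 0.25 | 8.6% | 12.4% |
| 50 | 0.50 | 20.1% | 35.3% |
| 200 | 0.25 | 20.1% | 35.3% |
| 200 | 0.50 | 60.9% | 88.5% |

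The result depends mainly on n and s, about which the protocol says nothing. The formula is also a two-time-point test, whereas the plan calls for repeated-measures or mixed models.

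**The case against.** **A contrast is intended.** Study Design sets routine time beside exposure periods, and Study Population expects exposure to vary. A reader might infer that the study has no unexposed reference period at all. The text does not support that: a within-person contrast is envisaged, but it is left undefined. This changes the description of the gap without closing it, because periods that are neither defined nor dated cannot be compared.

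**The plan does more than track time.** It also allows biomarker-psychometric correlations, so it would be wrong to say that it can show nothing but drift. Those correlations do not address the primary objective.

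**Exposure could still be obtained.** The questionnaire list is open-ended, and a market series could be linked by date afterwards. So the supportable statement is that exposure is not specified, and not that it is impossible to obtain. Even so, permissive wording commits the study to nothing. An index, threshold or lag chosen after outcomes are seen invites selective analysis, and market data would leave the informational part unmeasured.

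**A separate SAP may name the model term.** This has some force for the missing covariate, although the version history records that a statistical analysis plan was added in version 3.0, so that section may be the plan itself. It has little force for the data. A SAP can choose terms, but it cannot analyse individual media or economic exposure that was not collected. The point therefore rests mainly on the Primary Objective, Study Design and Study Population sections.

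**The percentages rest on invented inputs.** This stands in full. Nothing in the eligibility criteria selects people for high stress, so a 0.5 SD shift is only one possibility.

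**Conclusion.** The point holds in this form: exposure is named in the objective, the design and the population, but it has no specified definition, measure, source or dating, and no outcome is analysed against it. Followed as written, the plan gives time trends and outcome-to-outcome correlations, and the primary objective cannot be answered. That conclusion needs no numerical assumption and should be settled before data collection.

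The size of the false-attribution risk is unknown. Under the assumptions tried it runs from 5% to 88.5%. A reader might take the upper figures as this study's error rate, but the protocol supplies neither the sample size nor the baseline shift that produce them. They show that the mechanism can matter, not how much it does here.

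**What to change.** **Study Design.** Before data collection, define the exposure, its source and its time resolution. For the financial part, one option is a pre-named public daily market-volatility index linked by calendar date. For the informational part, one option is a brief self-report item or a screen-time log of financial and news media use. Other sources would serve if they are fixed in advance.

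**Statistical Analysis Plan section.** Make the primary analysis the association of each primary outcome with this time-varying exposure, adjusted for study time, with exposure preceding the outcome. Where exposure differs between people, separate the within-person from the between-person component. Use daily exposure for the three wearable primary outcomes. PSS-10 is given at scheduled intervals, so relate it to exposure aggregated over the preceding interval. Report the plain time trend as descriptive. The exact random-effects structure can be left to the statistician.

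**Alternative.** If exposure will not be measured, reword the Primary Objective to change over time only.

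**Cost.** A protocol amendment, some data linkage and a slight participant burden. A market index takes the same value for everyone on a given date, so its precision depends on the number of calendar dates observed. The protocol states no study duration, so duration should be considered when the exposure is chosen.

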### Secondary Objectives

- Evaluate sleep quality and sleep efficiency changes
- Assess anxiety symptom severity
- Assess perceived stress burden
- Correlate physiologic biomarkers with psychometric outcomes

### Study Design

This study is a prospective decentralized observational study utilizing wearable biosensor monitoring and validated psychometric questionnaires. Participants will undergo remote physiologic monitoring during routine daily activities and periods of financial or informational stress exposure. Commercially available wearable devices may be utilized to collect:

- Heart rate variability

- Resting heart rate
- Sleep duration
- Sleep efficiency
- Electrodermal activity
- Activity metrics

Validated questionnaires including the Generalized Anxiety Disorder-7 (GAD-7) and Perceived Stress Scale-10 (PSS-10) may be administered electronically during scheduled study intervals.

## Study Population

Adult participants exposed to varying levels of financial market activity, occupational stress, economic stress environments, and digital media exposure may be enrolled.

## Inclusion Criteria

- Adults age 18 years or older
- Ability to provide informed consent
- Access to compatible wearable biosensor technology
- Ability to complete electronic questionnaires

## Exclusion Criteria

- Conditions significantly impairing participation
- Current incarceration or institutionalization
- Participation in conflicting interventional studies

## Primary Outcome Measures

### Change in Heart Rate Variability (HRV)

Heart rate variability will be quantified using root mean square of successive differences (RMSSD) measured in milliseconds using wearable electrocardiographic or photoplethysmographic devices. Higher RMSSD values generally indicate lower physiologic stress burden and improved autonomic flexibility.

### Change in Sleep Duration

Sleep duration will be measured in hours per night using wearable sleep monitoring devices.

### Change in Resting Heart Rate

Resting heart rate will be measured in beats per minute using wearable biosensor devices.

### Change in Perceived Stress Scale-10 (PSS-10) Total Score

The validated 10-item Perceived Stress Scale questionnaire will be utilized. Scores range from 0 to 40, with higher scores indicating greater perceived psychological stress and worse outcomes.

## Secondary Outcome Measures

**Change in Sleep Efficiency**

Sleep efficiency percentage measured using wearable sleep tracking systems.

**Change in Galvanic Skin Response (GSR)**

Electrodermal activity measured in microsiemens using wearable biosensor devices to assess sympathetic nervous system activation.

**Change in Generalized Anxiety Disorder-7 (GAD-7) Total Score**

The validated GAD-7 questionnaire will be utilized. Scores range from 0 to 21, with higher scores indicating greater anxiety symptom severity and worse psychological outcomes.

**Statistical Analysis Plan**

Descriptive statistics will summarize baseline physiologic and demographic characteristics. Continuous physiologic variables including heart rate variability, sleep duration, sleep efficiency, resting heart rate, and galvanic skin response will be analyzed using longitudinal repeated-measures approaches and mixed-effects regression models where appropriate. Psychometric questionnaire outcomes including GAD-7 and PSS-10 scores will be analyzed longitudinally across study intervals. Correlation analyses may evaluate associations between physiologic biomarkers and psychometric stress measures. Missing data may be addressed through mixed-model maximum likelihood estimation or multiple imputation methods depending on missingness patterns. Statistical significance will utilize a two-sided alpha threshold of 0.05.

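### Four primary outcomes share one undivided two-sided 0.05 threshold, with no order, adjustment or rule for what counts as a positive primary finding

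*Protocol*

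**What the plan says.** Under the plural heading "Primary Outcome Measures" the protocol sets out four outcomes, each with its own subheading: heart rate variability measured as RMSSD, "Change in Sleep Duration", "Change in Resting Heart Rate" and "Change in Perceived Stress Scale-10 (PSS-10) Total Score". The heading "Secondary Outcome Measures" follows directly, so the primary list is exactly four.

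The Statistical Analysis Plan section says that the physiologic variables "will be analyzed using longitudinal repeated-measures approaches and mixed-effects regression models where appropriate". PSS-10 is handled in a separate sentence, together with GAD-7, as a longitudinal analysis. The section closes with its only statement on error rates: "Statistical significance will utilize a two-sided alpha threshold of 0.05". That threshold is not tied to any one outcome and is not divided. The section names no lead outcome, testing order, multiplicity method, or rule on whether one or all four primaries must be significant.

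The Version History records that the analysis plan was added to this document in version 3.0.

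**The concern.** With four primaries and one blanket threshold, the natural reading is that each outcome is judged at 0.05. The protocol then leaves open what a positive primary result would be. If one significant outcome is enough, the error rate of the primary claim is not the 0.05 that a reader sees, and one nominal hit out of four could be presented as the study's primary finding.

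The objectives do not settle the matter. The Primary Objective speaks of autonomic and physiologic biomarkers in general. Perceived stress stands under Secondary Objectives, yet PSS-10 is listed as a primary outcome. So the text does not show which outcome carries the primary claim, and a choice made after results are seen would give no error control.

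**Working it through.** **Inputs from the protocol**
- Number of primary outcomes: 4 (Primary Outcome Measures).
- Significance threshold: two-sided 0.05, undivided (Statistical Analysis Plan).
- Correlations between outcomes, sample size and power: not given.

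The protocol states no familywise error rate, so there is no derived figure to reproduce. The 0.05 is an input.

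**Assumptions**
- One test per outcome.
- All four null hypotheses true.
- Any one p-value below 0.05 counts as a positive primary finding.

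**Step 1: independent outcomes.** Familywise error = 1 − (1 − 0.05)^4 = 1 − 0.8145 = 0.1855, about 18.5%.

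**Step 2: correlated outcomes.** The protocol gives no correlations, so a range is shown. Four jointly normal test statistics with a common pairwise correlation were simulated, with 1,000,000 draws per value:

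| Pairwise correlation | Chance of at least one false primary finding |
|---|---|
| −0.3 | 17.1% |
| 0 | 18.6% (exact value 18.5%) |
| 0.3 | 17.4% |
| 0.5 | 15.6% |
| 0.7 | 13.1% |
| 0.9 | 9.4% |

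**Step 3: upper limits.** For jointly normal statistics and two-sided tests, the independent case is the maximum (Sidak inequality), so 18.5% is the ceiling there. With no assumption on dependence, the bound is 4 × 0.05 = 20%. Both limits hold only for one test per outcome. The analysis section does not fix which interval or model term is tested, and testing several would raise the rate.

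**Step 4: effect of dividing alpha.** The first Holm step is 0.05/4 = 0.0125. With all four nulls true, Holm makes a false claim only if the smallest p-value is at or below 0.0125. If the outcomes are independent, that chance is 1 − (1 − 0.0125)^4 = 4.91%. It is at most 4 × 0.0125 = 5% under any dependence.

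**Step 5: power cost.** The protocol states no power, so 80% at two-sided 0.05 is assumed for illustration.
- That power corresponds to a standardised effect of 1.9600 + 0.8416 = 2.8016.
- The two-sided critical value at 0.0125 is 2.4977.
- Power at 0.0125 = Φ(2.8016 − 2.4977) = Φ(0.3039) = 0.62.

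This is the worst case, because the later Holm steps use larger thresholds (0.05/3 = 0.0167, 0.05/2 = 0.025, then 0.05).

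**The case against.** The strongest reply is that the protocol never says that one significant outcome makes the study positive, and never says that 5% is the error rate across the four primaries. Both points stand. A reader might infer that the protocol adopts a rule of success on any one primary, or that it misstates its familywise error. The text supports neither: it gives a threshold and no success criterion. If all four outcomes had to be significant, there would be no inflation. The concern is that the protocol does not say which reading applies.

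A second reply is that the study is observational, that its stated aim is to evaluate changes, and that no confirmatory claim is announced. Whether outcomes reported separately in such a study need familywise control is partly a matter of judgement. This lowers the consequence. It does not change the arithmetic, because the document does designate primaries and does set a significance threshold.

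A third reply is that multiplicity is commonly left to a separate analysis plan, which may exist. It may, so one cannot be sure that no control is planned. But this document carries its own Statistical Analysis Plan section and fixes the significance rule there. The fault is a stated rule that does not fit the stated outcomes, and not only a missing detail.

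One might also quote 1 − 0.95^7 = 30.2% across all seven listed outcomes. Three of those are secondary, so that figure says nothing about the primary claim.

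**Conclusion.** The point holds as a moderate issue. The four primaries and the single undivided 0.05 do not fit together without a decision rule. If any one significant primary is taken as a positive finding, the chance of at least one false primary finding is about 18.5% with independent outcomes and about 13% to 17% at correlations of 0.7 to 0.3. These figures assume one test per outcome, all four nulls true and jointly normal statistics.

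A reader might take 18.5% as an absolute ceiling. It is not: without the normality assumption the bound is 20%, and several tests per outcome could push the rate higher. Strong positive correlation would bring it lower. Because the protocol makes no familywise claim and the design is observational, the gap should be closed, but it does not invalidate the plan.

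**What to change.** In the Statistical Analysis Plan section, prespecify one test for each primary outcome (one contrast or model term at one time point or interval). State that the four listed primaries are tested with Holm's procedure at familywise two-sided 0.05. The smallest p-value is compared with 0.0125 and the next with 0.0167, 0.025 and 0.05 in turn, stopping at the first that fails. The list under Primary Outcome Measures stays as it is.

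The cost is wording plus some power: in the worst case, 80% at 0.05 becomes about 62% at 0.0125. No extra data or procedures are needed.

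Alternatively, the sponsor may name one primary outcome before any data are seen and state the status of each of the others. That must include PSS-10, whose subject the Secondary Objectives already treat as secondary. This keeps the full 0.05 for the named outcome, but it means rewriting the primary outcome list. If the remaining outcomes are tested in a fixed order, a later one cannot be claimed once an earlier one fails.

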**Ethics and Human Subjects Protections**

This observational study will be conducted in accordance with applicable human subjects research standards and ethical principles described in the Declaration of Helsinki. Participation is voluntary and participants may withdraw at any time. Data collected from wearable monitoring devices and questionnaires will be de-identified prior to analysis where applicable.

**Version History**

Version	Date	Description
1.0	May 20, 2026	Initial Draft
2.0	May 24, 2026	PRS Revisions
3.0	May 27, 2026	Statistical Analysis Plan Added
